The most common adverse reactions (greater than or equal to 20%) were diarrhea, hypertension, hair color changes, nausea, anorexia, and vomiting. Grade 3/4 adverse reactions that differed by greater than or equal to 2% between arms were abnormal hepatic function, diarrhea, hypertension, and proteinuria. QT prolongation has been seen with pazopanib. Laboratory abnormalities occurring in >10% of patients and more commonly (>5%) in the pazopanib arm included increased transaminases, hyperglycemia, leukopenia, hyperbilirubinemia, neutropenia, hypophosphatemia, thrombocytopenia, lymphocytopenia, hyponatremia, hypomagnesemia, and hypoglycemia. Deaths due to serious adverse events include cerebrovascular accident, gastric cancer, gastrointestinal hemorrhage, hemoptysis, bowel perforation, cardiac failure, myocardial infarction, hepatic failure and pneumonia occurred more commonly in the pazopanib arm. Hepatic dysfunction is included as a boxed warning in the product label and two deaths were associated with hepatic failure.

Recently, a phase II trial was designed for patients with metastatic breast cancer, who failed 2-3 prior chemotherapy. Total 20 patients were recruited in this study, 70% were ER+, and all were Her-2/neu negative. Pazopanib monotherapy was given at 800 mg daily. One patient (5%) had a partial response, 11 (55%) had stable disease (SD) [four (20%) with SD > or = 6 months], and seven (35%) had progressive disease as their best response. One (5%) was not evaluable. The median time to progression was 5.3 months. Pazopanib did not cause significant severe toxicity aside from grade 3-4 transaminitis, hypertension, and neutropenia in three patients each (14% each) and grade 3 gastrointestinal hemorrhage in one patient (5%)[18].

Standard therapy for hormone receptor positive metastatic disease.

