b.	Well-controlled BP defined as mean SBP \leq 150 mmHg and mean DBP \leq 90 mmHg.
c.	AEs are graded according to NCI Common Terminology Criteria for Adverse Events v4.0 (NCI CTCAE v4) for the management of treatment related diarrhea, please refer to Appendix III. Abbreviations: BP, blood pressure; PAZOPANIB, investigational product.

Dose Interruptions/Modifications for Hepatotoxicity

Recommendations for investigational product dose interruptions/modifications in case of liver-related treatment-emergent AEs are provided in Table 3. As a general rule, since many subjects are taking multiple concurrent medications, it is critical to (a) do a thorough evaluation of the subject's concurrent medications, and (b) identify and discontinue those with known hepatotoxicity and replace with a non-hepatotoxic equivalent for the same indication if necessary.

Table 3 Guidelines for Management of Treatment Emergent Hepatotoxicity

Event	Dose Modification Algorithms
(A). ALT of $\leq 3.0 \times$ upper limit of normal (ULN)	Continue IP at current dose with full panel liver function tests (LFTs) ^a monitored as per protocol.
(B). ALT $>3.0 \times$ ULN to $\leq 8.0 \times$ ULN without bilirubin elevation (defined as total bilirubin $<2.0 \times$ ULN or direct bilirubin $\leq 35\%$) and without hypersensitivity symptoms (e.g., fever, rash)	
1. Continue pazopanib at current dose.2. Work up for other etiologies as clinically indicated.3. Monitor subject closely for clinical signs and symptoms; perform full panel LFTs weekly or more frequently if clinically indicated until alanine aminotransferase (ALT)/aspartate aminotransferase (AST) reduced to Grade 1.

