(C). ALT $>8.0 \times$ ULN without bilirubin elevation (defined as total bilirubin $<2.0 \times$ ULN or direct bilirubin $\leq 35\%$) and without hypersensitivity symptoms (e.g., fever, rash), not attributed to malignancy.	
1st occurrence
 
1. Discontinue pazopanib until toxicity resolves to \leq Grade 1 or baseline. Report the event to Novartis as an SAE within 24 hours of learning of its occurrence (section 16.2, SAE reporting), and complete the eCRF liver event forms. Make every reasonable attempt to have subjects return to the clinic within 24 to 72 hours for repeat liver chemistries and liver event follow up assessments. Pazopanib may only be restarted following recovery if toxicity is clearly unrelated to study drug (e.g. alcohol or significant acetaminophen ingestion)2. Work up for other etiologies as clinically indicated .3. Monitor subject closely for clinical signs and symptoms; perform full panel LFTs weekly or more frequently if clinically indicated until alanine aminotransferase (ALT)/aspartate aminotransferase (AST) reduced to Grade 1.

Event	Dose Modification Algorithms
(D). ALT >3.0 x ULN with concomitant elevation in bilirubin (defined as total bilirubin <2.0 x ULN; with direct bilirubin >35%) not related to disease progression, or with hypersensitivity symptoms (e.g., fever, rash).	
 1. Discontinue pazopanib immediately, report the event to Novartis as an SAE within 24 hours of learning of its occurrence (section 16.2, SAE reporting), and complete the eCRF liver event forms. Make every reasonable attempt to have subjects return to the clinic within 24 hours for repeat liver chemistries and liver event follow up assessments. 2. Consult a gastroenterologist / hepatologist and perform the following assessments to identify potential co-factors: 
 • Eosinophil count • Viral serology for hepatitis A, B, C and E, cytomegalovirus, Epstein-Barr virus IgM antibody, or heterophile antibody, or monospot testing) • Anti-nuclear antibody, anti-smooth muscle antibody, anti-mitochondrial antibody • Serum creatinine phosphokinase for possible muscle injury caused LFT elevation • Liver imaging (ultrasound or CT scan) 3. Monitor subject closely for clinical signs and symptoms; perform full panel LFTs weekly or more frequently if clinically indicated until LFTs reduced to Grade 1.

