All SAEs	24 hours	SAE data collection tool	24 hours	Updated SAE data collection tool
Pregnancy	2 weeks	Pregnancy Notification Form	2 weeks	Pregnancy Follow up Form
Liver chemistry abnormalities:				

ALT: >3.0 x ULN with concomitant elevation in bilirubin ^a (defined as total bilirubin \geq 2.0 x ULN with direct bilirubin >35%) or with hypersensitivity symptoms (e.g., fever, rash).	24 hours	SAE data collection tool. ^b Liver Event Case Report Form (CRF) and liver imaging and/or biopsy CRFs if applicable	24 hours	Updated SAE data collection tool. ^b Updated Liver Event CRF
ALT >8.0 x ULN without bilirubin elevation (defined as total bilirubin $<$ 2.0 x ULN or direct bilirubin \leq 35%) and without hypersensitivity symptoms (e.g., fever, rash)	24 hours	SAE data collection tool. Liver Event CRF ^b	24 hours	Updated SAE data collection tool. Updated Liver Event CRF ^b

- a. Bilirubin fractionation should be performed if testing is available. If testing is unavailable and a subject meets the criterion of total bilirubin \geq 2.0 x ULN, then the event should be promptly reported as defined.
- b. Liver event documents should be completed as soon as possible.

All Events must be reported to Novartis within 24 hours of learning of its occurrence. Information about all SAEs is collected and recorded on a Serious Adverse Event Report Form; all applicable sections of the form must be completed in order to provide a clinically thorough report. The investigator must assess and record the relationship of each SAE to each specific study treatment (if there is more than one study treatment), complete the SAE Report Form in English, and send the completed, signed form by **fax within 24 hours to the oncology Novartis DS&E department with the provided FAX cover sheets.**

- Novartis DS&E Oncology Department - [REDACTED]

SAEs brought to the attention of the Study Chair at any time after cessation of pazopanib and considered by the Study Chair to be related or possibly related to pazopanib must be reported to Novartis Pharmaceuticals if and when they occur. Additionally, in order to fulfill international reporting obligations, SAEs that are related to study participation (e.g., procedures, invasive tests, change from existing therapy) or are related to a concurrent medication will be collected and recorded from the time the subject consents to participate in the study until he/she is discharged.

Review of Adverse Event Rates

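### Table 3 gives no instruction for ALT above 8 x ULN that is attributed to malignancy and occurs without hypersensitivity symptoms, and its reporting scope for ALT above 8 x ULN differs from Section 16.2.2

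*Combined protocol and SAP*

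**What the plan says.** Table 3 (Section 7.0, hepatotoxicity) sorts events by ALT, bilirubin and hypersensitivity symptoms.

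- Row (A), ALT up to 3 x ULN: "Continue IP at current dose with full panel liver function tests". Attribution is not mentioned.
- Row (B), ALT >3 to 8 x ULN without bilirubin elevation or hypersensitivity: "Monitor subject closely for clinical signs and symptoms; perform full panel LFTs weekly or more frequently if clinically indicated". Attribution is not mentioned.
- Row (C), ALT above 8 x ULN without bilirubin elevation "and without hypersensitivity symptoms (e.g., fever, rash), not attributed to malignancy". This row contains the action on study drug, the liver-test interval, the 24-hour SAE report to the manufacturer and the liver event forms.
- Row (D), ALT above 3 x ULN with a bilirubin elevation "not related to disease progression, or with hypersensitivity symptoms".
- The last row, on isolated bilirubin elevation, applies only when ALT is below 3 x ULN.

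Table 2 is confined to toxicities that are not liver related.

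The liver table in Section 16.2.2 lists "ALT >8.0 x ULN without bilirubin elevation", with the same bilirubin and hypersensitivity conditions as row (C), for reporting within 24 hours. It has no malignancy exclusion. The same section requires SAE reports irrespective of relationship to study drug.

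**The concern.** Two things do not fit together. First, the instructions stop as severity rises. An isolated ALT of, say, 5 x ULN thought to come from liver metastases has a row and at least weekly tests; an isolated ALT above 8 x ULN with the same attribution has no row. Second, the 24-hour reporting instruction for ALT above 8 x ULN has two scopes: conditional on attribution in Table 3, unconditional in Section 16.2.2.

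This is an open-label, single-arm, two-site trial in advanced breast cancer, so attributing raised ALT to the cancer is an unblinded judgement. Row (C) does not say who makes that judgement or on what evidence. Safety is a secondary endpoint, and Section 1.2 says of the drug: "Hepatic dysfunction is included as a boxed warning in the product label and two deaths were associated with hepatic failure". Sites that work from different parts of the protocol could handle the same laboratory value differently.

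**Working it through.** The plan states no figure on this point, so there is none to reproduce. The check is a side-by-side reading of the two tables.

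**Inputs.** Table 3 rows (A) to (D) as printed, and the two liver rows of the Section 16.2.2 table. Both places define no bilirubin elevation as total bilirubin below 2 x ULN or direct bilirubin at most 35%. Row (D) as printed defines elevation the other way on total bilirubin: "defined as total bilirubin <2.0 x ULN; with direct bilirubin >35"%. Section 16.2.2 uses total bilirubin of at least 2 x ULN with direct above 35%.

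**Assumption.** Attributed to malignancy (row C) is taken as equivalent to related to disease progression (row D).

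**Cases without hypersensitivity symptoms:**

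| Total bilirubin (x ULN) | Direct bilirubin | Table 3: ALT >3 to 8, attributed to malignancy | Table 3: ALT >8, not attributed | Table 3: ALT >8, attributed to malignancy | Section 16.2.2: ALT >8, either attribution |
|---|---|---|---|---|---|
| <2 | ≤35% | B | C | none | ALT >8 row |
| <2 | >35% | B | C and D | none | ALT >8 row |
| ≥2 | ≤35% | B | C | none | ALT >8 row |
| ≥2 | >35% | none | none | none | ALT >3 with bilirubin row |

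**Cases with hypersensitivity symptoms.** Row (D) has a second limb for these, and on its natural reading the progression exclusion does not reach it. All 4 bilirubin patterns at ALT above 8 x ULN therefore fall in row (D), whatever the attribution. All 4 are also reportable under Section 16.2.2.

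**Reading the result.**

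1. For ALT above 8 x ULN attributed to malignancy, 4 of 8 combinations have no Table 3 row: all 4 without hypersensitivity. All 8 have a 24-hour reporting row in Section 16.2.2.
2. In the first three lines of the table, attribution is what removes the row, because the same values not attributed to malignancy fall in row (C). The fourth line has no row under either attribution. That comes from the bilirubin definition in row (D), a separate conflict in the same table.
3. At the lower ALT range with the same attribution, row (B) applies in 3 of 4 patterns. In those three, the lower value has an instruction and the higher one has none.
4. If the assumption is relaxed, so that a rise can be due to malignancy without being progression, the second line falls in row (D). The first and third lines still have no row.

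**The case against.** The strongest reply is that the exclusion is deliberate. Table 3 offers guidance on treatment-emergent hepatotoxicity, and a rise caused by the cancer is arguably outside it. Dose rules and safety reports serve different purposes and may have different scopes. Silence in a dose-modification table cannot override an explicit reporting table, and rows (C) and (D) both point the reader to Section 16.2.

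Much of this stands. Three stronger conclusions that a reader might draw are not supported:

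- **That Table 3 omits these events altogether.** Row (D) keeps those with hypersensitivity symptoms.
- **That the patient goes without management.** Section 7.0 requires laboratory abnormalities to be evaluated at each visit, causes to be investigated and, for liver events, concurrent medication to be reviewed. Liver tests continue at weeks 3, 5, 7 and 9, then every 4 weeks, and when clinically indicated. Visits may become monthly only in stable patients without grade 2 or greater toxicity. What is missing is a Table 3 instruction, not care.
- **That the event goes unreported.** No combination with ALT above 8 x ULN escapes Section 16.2.2.

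The deliberate-exclusion argument does not close the gap, for three reasons. Section 16.1.1 defines adverse events irrespective of causality and includes worsening of a condition present at baseline. Entry requires ALT of at most 2.5 x ULN, so any value above 8 x ULN is more than 8 / 2.5 = 3.2 times the entry limit. And row (C) retains other causes unrelated to the drug: its alcohol and acetaminophen examples bear only on restarting. If malignancy is meant to be treated differently, the protocol does not say what then applies.

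On reporting, a limited risk remains. Section 16.1.3 does not name ALT above 8 x ULN among its seriousness criteria, so the specific trigger for this laboratory value lies in row (C) and in the Section 16.2.2 table, whose scopes differ.

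**Conclusion.** The point holds as a gap in Table 3 and an inconsistency in scope between Table 3 and Section 16.2.2. ALT above 8 x ULN attributed to malignancy, without hypersensitivity symptoms, has no Table 3 row, while the lower range has one. The 24-hour report is mandatory under Section 16.2.2 but conditional in row (C), so a site relying on Table 3 could miss it.

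The size is a class of events, not a number of patients: 4 of 4 bilirubin patterns under the stated assumption, three of them because of attribution. It may be tempting to multiply published rates of Grade 3–4 ALT elevation by an assumed share attributed to malignancy. The documents give neither that share nor the proportion above 8 x ULN, so such a count would have no basis.

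The primary endpoint, sample size and two-stage decision rule are unaffected. The correction is worth making because hepatic dysfunction is the boxed-warning risk and the change is small. No view is taken on which clinical rule is right.

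**What to change.** Reconcile Table 3 rows (C) and (D) with the Section 16.2.2 liver table so that:

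- every ALT value above 8 x ULN has an instruction in Table 3, including values attributed to malignancy;
- the 24-hour reporting scope is the same in both places, with an explicit statement of whether attribution to malignancy or progression changes it;
- the protocol says who makes the attribution and requires its basis to be recorded.

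Settle the bilirubin definition in row (D) in the same edit, since it conflicts with Section 16.2.2 and leaves a further pattern without a row. What each row instructs is for the sponsor to decide.

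The cost is protocol wording plus one recorded item for each such event. No change to the design or analysis is needed.

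### Table 3 row (D) reverses the total-bilirubin threshold, so combined ALT and conjugated-bilirubin elevation has no dosing rule and a milder pattern has two opposite ones

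*Combined protocol and SAP*

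**What the plan says.** Table 3 in Section 7.0 sorts treatment-emergent liver abnormalities by ALT, bilirubin and hypersensitivity symptoms, and attaches a dosing action to each row.

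- **Row (B)**, ALT above 3 and up to 8 x ULN, applies "without bilirubin elevation (defined as total bilirubin $<2.0 \times$ ULN or direct bilirubin $\leq 35\%$) and without hypersensitivity symptoms". Its first instruction is "Continue pazopanib at current dose".
- **Row (C)**, ALT above 8 x ULN, applies "without bilirubin elevation (defined as total bilirubin $<2.0 \times$ ULN or direct bilirubin $\leq 35\%$) and without hypersensitivity symptoms (e.g., fever, rash), not attributed to malignancy". Pazopanib is stopped until recovery and may be resumed only if the study drug is clearly not the cause.
- **Row (D)** applies to "ALT >3.0 x ULN with concomitant elevation in bilirubin (defined as total bilirubin <2.0 x ULN; with direct bilirubin >35" per cent, "not related to disease progression, or with hypersensitivity symptoms (e.g., fever, rash"). Its first instruction is "Discontinue pazopanib immediately, report the event to Novartis as an SAE within 24 hours of learning of its occurrence". Repeat chemistries within 24 hours, a specialist consultation and an aetiological work-up follow.
- **The last row**, isolated bilirubin elevation, is limited to ALT below 3 x ULN.

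The liver table in Section 16.2.2 makes ALT above 3 x ULN with a concomitant bilirubin elevation reportable within 24 hours. There the elevation is "defined as total bilirubin \geq 2.0 x ULN with direct bilirubin >35" per cent. Footnote a to that table again gives 2.0 x ULN or more as the total-bilirubin criterion.

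**The concern.** Row (D) defines an elevation by a ceiling. A patient with normal total bilirubin satisfies it if the direct fraction exceeds 35%, while a patient with total bilirubin of 5 x ULN does not. This contradicts rows (B) and (C) of the same table and the definition in Section 16.2.2.

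Table 3 is the part of the protocol that tells a site whether to continue pazopanib after a liver signal. Section 1.2 records that hepatic dysfunction carries a boxed warning and that two deaths were associated with hepatic failure. The pattern that loses its dosing rule, raised ALT with raised conjugated bilirubin, is the one row (D) exists to catch. Two sites working from a table with a gap and a contradiction may also handle similar patients differently, which would blur the exposure and safety data.

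**Working it through.** No sample size or error rate is involved. The check is whether the rows, taken as logical conditions, cover every patient exactly once.

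**Notation.** ALT and total bilirubin T are in multiples of ULN. F is the direct fraction of bilirubin. Start with patients who have no hypersensitivity symptoms and whose abnormality is not attributed to malignancy or progression.

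**Conditions as written**

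| Source | Condition | Action |
|---|---|---|
| Table 3 (A) | ALT ≤ 3 | continue |
| Table 3 (B) | 3 < ALT ≤ 8 and (T < 2 or F ≤ 35%) | continue |
| Table 3 (C) | ALT > 8 and (T < 2 or F ≤ 35%) | stop, conditional restart |
| Table 3 (D) | ALT > 3 and T < 2 and F > 35% | stop at once, no restart rule given |
| Table 3, isolated bilirubin | ALT < 3 | no dose change for isolated elevation |
| Section 16.2.2 | ALT > 3 and T ≥ 2 and F > 35% | report within 24 hours |

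**Step 1: what row (D) has to be.** Rows (B) and (C) define no elevation as (T < 2 or F ≤ 35%). The negation is (T ≥ 2 and F > 35%). That is the Section 16.2.2 definition exactly. Row (D) instead has (T < 2 and F > 35%), which is a subset of no elevation.

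**Step 2: classify test cases under the text as written.** ALT is 5 or 10, T is 0.8, 1.5, 2 or 3, and F is 20% or 50%, giving 2 x 4 x 2 = 16 combinations.

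| ALT | T | F | Rows matched as written | Rows matched if (D) has T ≥ 2 |
|---|---|---|---|---|
| 5 | 0.8, 1.5 | 50% | (B) continue and (D) stop | (B) |
| 5 | 2, 3 | 50% | none | (D) |
| 10 | 0.8, 1.5 | 50% | (C) and (D) | (C) |
| 10 | 2, 3 | 50% | none | (D) |
| 5 | all four | 20% | (B) | (B) |
| 10 | all four | 20% | (C) | (C) |

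As written, 4 of the 16 match no row, 4 match two rows, and 8 match one. Of the 4 double matches, 2 (ALT 5) carry opposite instructions. In the other 2 (ALT 10) both rows stop the drug and differ only on restart. With T ≥ 2 in row (D), all 16 match exactly one row.

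**Step 3: hypersensitivity symptoms.** These patients enter row (D) through its alternative clause whatever the bilirubin, so the gap and the overlap do not apply to them.

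**Step 4: cases attributed to malignancy or progression.** Rows (C) and (D) carry exclusions for these. Without hypersensitivity symptoms, 10 of the same 16 combinations match no row: all 8 at ALT 10, and the 2 at ALT 5 with T ≥ 2 and F = 50%. The count is still 10 after the sign is corrected, so this is a separate matter.

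**Step 5: whether another rule fills the gap.** Table 2 is restricted to non-liver toxicities. Section 16.2.2 requires reporting but gives no dosing instruction.

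**Step 6: frequency.** Section 1.2 gives concomitant transaminase and bilirubin elevation in under 1% of subjects. For 30 enrolled, that is fewer than 30 x 0.01 = 0.3 patients in the gap. The overlap starts from a commoner event: Section 11.1.4 gives ALT above 3 x ULN in 126/895 = 14% on pazopanib without a statin, or 30 x 0.14 = 4.2 patients. Only those with F > 35% and T < 2 would be in the overlap, and the documents do not give that share. It could be anywhere from none to all of the 4.2.

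**The case against.** The strongest reply is that this is a one-symbol slip whose meaning can be recovered. The row calls itself an elevation, every other definition in the protocol agrees on 2.0 x ULN or more, and a clinician facing ALT above 3 x ULN with conjugated bilirubin of twice normal would be unlikely to conclude that bilirubin was not raised. That is a fair account of how the error probably arose. It does not supply the missing rule, because a stopping table is there so that sites need not infer it.

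Four narrower points also have some force.

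- **Reporting survives.** The uncovered patient is still a 24-hour reportable event under Section 16.2.2, so what is missing is the Table 3 dosing action and work-up, not all action.
- **The direct conflict is limited.** Opposite instructions arise only for ALT above 3 and up to 8 x ULN. Moreover, the liver panel listed in Section 8 includes total but not direct bilirubin, so at totals below 2.0 x ULN the fraction will often be unknown and the overlap unseen. This reduces the practical reach of the overlap but not of the gap.
- **The numbers are small.** With fewer than 0.3 expected patients in the gap, the primary endpoint and the decision rule are untouched. The case for correction rests on the severity of the event.
- **The text was read from a PDF.** A misread sign cannot be excluded from the text alone. However, the other inequality signs in the row (D) cell came through sensibly, and the sign for at or above survives in Section 16.2.2. The original page should be checked.

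**Conclusion.** The concern holds. On the text as supplied, row (D) of Table 3 states the total-bilirubin condition in reverse. For patients without hypersensitivity symptoms, and with the abnormality not attributed to malignancy or progression:

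- ALT above 3 x ULN, total bilirubin 2.0 x ULN or more and direct above 35% has no Table 3 dosing action.
- ALT above 3 and up to 8 x ULN, total below 2.0 x ULN and direct above 35% has two opposite actions.
- ALT above 8 x ULN with that same bilirubin pattern has two rows that agree on stopping but not on restart.

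The expected count in the gap is below 0.3 of 30, assuming that the rate quoted in Section 1.2, from renal cell cancer patients on monotherapy, carries over to this population and combination. The count in the overlap cannot be derived from the documents. Despite the low frequency this must be fixed, because it is a stopping rule for a potentially fatal, boxed-warning toxicity. The conclusion also assumes that the sign in the original page is as it reads here.

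**What to change.** Confirm the sign on the original page, then change row (D) of Table 3 to total bilirubin at or above 2.0 x ULN with direct bilirubin above 35%, as in Section 16.2.2. If the clinical team wants a different threshold, it should be written once and used in rows (B), (C), (D) and Section 16.2.2 alike. Then check that the rows cover every combination of ALT, total bilirubin and direct fraction once only.

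Two related points can go into the same amendment. Table 3 could say what to do when the direct fraction is unavailable, as footnote a in Section 16.2.2 does for reporting. The clinical team should also decide the action for liver abnormalities attributed to malignancy or progression, which the sign change does not settle.

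The core correction is one symbol in a protocol amendment with a letter to both sites, and adds no procedures or patients. The two related points need a few more lines and a clinical decision.
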